## 1. LIST OF ABBREVIATIONS

Abbreviation	Definition
ACR20	American College of Rheumatology 20% improvement criteria
ADR	Adverse drug reaction
AE	adverse event
AEM	adverse event monitoring
ANC	absolute neutrophil count
CRF	case report form
CRP	C-reactive protein
CYP	cytochrome P450
DAS	Disease Activity Score
DAS28	Disease Activity Score using 28 joint counts
DMARD	disease-modifying anti-rheumatic drug
EDP	exposure during pregnancy
EULAR	European League Against Rheumatism
ESR	erythrocyte sedimentation rate
GEP	Good Epidemiological Practice
GPP	Good Pharmacoepidemiology Practice
HDL	high density lipoprotein
IEA	International Epidemiological Association
IEC	Independent Ethics Committee
IRB	Institutional Review Board
ISPE	International Society for Pharmacoepidemiology

LDL	low density lipoprotein
MFDS	Ministry of Food and Drug Safety
NIS	non-interventional study
PhRMA	Pharmaceutical Research and Manufacturers Association
PMS	post-marketing surveillance
PsA	psoriatic arthritis
RA	rheumatoid arthritis
RMP	Risk Management Plan
SAE	serious adverse event
SAP	statistical analysis plan
SRSD	single reference safety document
SJC28	28 swollen joint count
TC	total cholesterol
TJC28	28 tender joint count
VAS	visual analogue scale
WHO-ART	World Health Organization - Adverse Reaction Terminology
Xeljanz®	tofacitinib citrate

### 3. AMENDMENTS AND UPDATES

Protocol Amendments 1 to 11 are summarized in the table below.

Amendment number	Date	Substantial or administrative amendment	Protocol section(s) changed	Summary of amendment(s)	Reason
Amendment 1	14 April 2015	Substantial	Section 5 Rationale and background Section 7 Research methods Section 8 Protection of human subjects Section 9 Management and reporting of adverse events/adverse reactions Section 11 References	

Change study design from retrospective to prospective.

Add more detailed data collection procedures.

Add the description of data privacy statement requirement and patient withdrawal.

Change safety language to prospective study.

Correct indication as per local product document.

Add MFDS guidelines as references.

	The design of the original protocol dated 28 October 2014 was not accepted by the MFDS. The protocol is amended to satisfy MFDS' requirements
Amendment 2	29 October 2015	Substantial	Section 1 List of abbreviations Section 4 Milestones Section 7.1 Study design Section 7.2.5.2 Demography and baseline characteristics Section 7.3.1.2 Laboratory test Section 7.3.2 Efficacy variables Section 7.7.1 Safety analysis Section 7.7.2 Efficacy analysis Section 9.4.2 Serious adverse events Section 11 References Section 12 List of tables	

Add some abbreviations.

Change planned date for end of data collection from 01 March 2020 to 01 April 2020.

Add recording medical histories of latent tuberculosis, renal disorder and hepatic disorder.

Add recommended laboratory tests.

Add efficacy variable ACR20, its definition, and assessment.

Add statement that SAEs such as serious infection, tuberculosis, cancer, or lymphocyte proliferative disorders will be considered as SAEs of special interest and summarized separately.

Add a reference about ACR20.

Add a list of tables.

	The protocol is amended to reflect MFDS' comments on Amendment 1.

Xeljanz® (tofacitinib citrate)  
A3921249 NON-INTERVENTIONAL STUDY PROTOCOL  
Amendment 11, 26 Apr 2022

Amendment 03	25 January 2016	Substantial	Section 7.2.2 Exclusion criterial Section 7.3.2 Efficacy Variables Section 7.6 Data management	
 
Change for exclusion criteria to clarify the standard according to dosage and administration
 
Add the investigators overall assessment about efficacy based on DAS 28 or ACR 20
 
Change the coding dictionary for Disease to WHO-ART.
 
	Clarification of exclusion criteria and efficacy assessment
Amendment 04	01 August 2016	Substantial	Section 7.2.2 Exclusion criterial Section 7.3.1.2 Laboratory Test Section 7.7.2. 7.7.2. Efficacy analysis	
 
Change the contents from exclusion criterial to Laboratory Test about drug discontinuation criterial in accordance with laboratory test result by MFDS requirements.
 
Include the contents of effectiveness ratio and less effectiveness ratio about overall efficacy assessment by MFDS requirement
 
	Amended to reflect MFDS' comments on Amendment 3
Amendment 05	11 December 2018	Substantial	Section 5 Rationale and background Section 7.1 Study design Section 7.5 Study size	
 
Considering the disease prevalence and status of administration, the number of target subjects is amended
 
	Amended to adjust the number of target subjects

Xeljanz® (tofacitinib citrate)  
A3921249 NON-INTERVENTIONAL STUDY PROTOCOL  
Amendment 11, 26 Apr 2022

		Administrative	Section 7.6 Data management	
 
Specified coding dictionary of concomitant medication as an ATC code.
 
	Specified conmed coding dictionary
Amendment 06	21 February 2019	Substantial	Section 7.2.1 Inclusion criteria Section 7.2.2 Exclusion criteria Section 7.2.4 Dosage and administration Section 7.2.5.2 Demography and baseline characteristics Section 7.3.2.1 Efficacy evaluation 7.4.1 Case report forms Section 8.1 Patient information Section Patient consent Section 8.4 institutional Review Board(IRB)/Independent Ethics Committee (IEC)	
 
Add new indications according to the updated label
 
	Add new indications (for psoriatic rheumatoid arthritis (PsA))
Amendment 07	17 June 2019	Substantial	Section 7.2.5.2 Demography and baseline characteristics	
 
Add the severity criteria of disease activity for PsA indication
 
	The protocol is amended to reflect MFDS' comments on Amendment 6.
Amendment 08	07 August 2019	Substantial	Study title Section 5 Rationale and background Section 7.1 Study design Section 7.2.3 Duration of the study Section 7.2.5 Study procedures Section 7.5 Study size	
 
Specify the indication in the title
 
Add abbreviations
 
Sample size adjust, add RMP scope
 
Add retrospective data collection method
 
	Target sample size adjustment, add RMP scope according to the MFDS comments.

Xeljanz® (tofacitinib citrate)  
A3921249 NON-INTERVENTIONAL STUDY PROTOCOL  
Amendment 11, 26 Apr 2022

Amendment 09	14 January 2020	Substantial	Section 4 Milestones Section 7.7.1 Safety analysis	
 
• Add RMP report submission timeline
 
• Add analysis and evaluation methods for safety specification according to RMP
 
	Amended according to the MFDS comments
Amendment 10	19 March 2020	Administrative  Substantial	Section 2 Responsible parties  Section 7.2.1 Inclusion criterial  Section 7.2.2 Exclusion criterial  Section 7.2.5.1 Information of Institution  Section 7.2.5.2 Demography and baseline characteristics	
 
• Change the non-interventional study lead
 
• Add the abbreviation
 
• Change the collected data
 
• Guidance for obtaining the data privacy statement in the subjects to be collected data retrospectively
 
• Change the collected data
 
	Coordination of internal task  Change of research methods
Amendment 11	26 Apr 2022	Minor	Section 2 Responsible parties  Section 4 Milestones  Section 5 Rationale and Background  Section 7.1 Study design  Section 7.2.3 Duration of the study  Section 7.5 Study size	
 
• Change of NISL
 
• Change of study period
 
	Coordination of internal task  Amended according to MFDS' comments

Abbreviations: ACR20=American College of Rheumatology 20% improvement criteria, MFDS=Ministry of Food and Drug Safety, SAE=serious adverse event.

#### 4. MILESTONES

Milestone	Planned date
Start of data collection	01 May 2015
End of data collection	01 April 2020
First year (1-1) periodic report (MFDS)	01 December 2014
First year (1-2) periodic report (MFDS)	01 June 2015
Second year (2-1) periodic report (MFDS)	01 December 2015
Second year (2-2) periodic report (MFDS)	01 June 2016
Third year annual report (MFDS)	01 June 2017
Fourth year annual report (MFDS)	01 June 2018
Fifth year annual report (MFDS)	01 June 2019
Final study report (MFDS)	01 July 2020
RMP periodic report will be submitted every year after RMP approval	

Abbreviations: MFDS=Ministry of Food and Drug Safety.

#### 5. RATIONALE AND BACKGROUND

Xeljanz® (tofacitinib) is a potent, oral janus kinase inhibitor. Xeljanz was approved by the Ministry of Food and Drug Safety (MFDS) on 02 April 2014 for the treatment of adult patients with moderately to severely active rheumatoid arthritis (RA) who have had an inadequate response or intolerance to methotrexate. It may be used as monotherapy or in combination with methotrexate or other nonbiologic disease-modifying anti-rheumatic drugs (DMARDs).

In addition, MFDS approved new indications for the treatment of adult patients with active psoriatic arthritis (PsA) who have had an inadequate response or intolerance to previous antirheumatic drugs (DMARDs) on 20 Sep 2018. It may be used in combination with methotrexate or other nonbiologic disease-modifying anti-rheumatic drugs (DMARDs). The efficacy of Xeljanz as a monotherapy has not been studied in psoriatic arthritis.

CCI

CCI

Background information on Xeljanz can be obtained from the current version of the local product document (ie, local labelling), which is the single reference safety document (SRSD) for information relating to Xeljanz in this study.

## 6. RESEARCH QUESTION AND OBJECTIVES

The objective of this study is to identify any problems and questions with respect to the safety and efficacy of Xeljanz during the post-marketing period as required by the regulation of MFDS.

## 7. RESEARCH METHODS

### 7.1. Study design

This is an open-label, non-comparative, non-interventional, prospective, and multi-center study conducted in Korean health care centers by accredited physicians (ie, investigators). The study population will be adult patients with moderately to severely active RA who have had an inadequate response or intolerance to methotrexate. Xeljanz will be administered according to the “Dosage and Administration” of the approved labeling. There is no visit or activity mandated by this study. The investigator will collect patient data and record the information on each patient’s case report form (CRF).

CCI

Also, investigators collect data on the Xeljanz retrospectively from the subjects who have been administered the Xeljanz according to the local product documents but not participated in this study until 26 June 2022.

Safety is the primary interest of this study, which will be assessed based on adverse events (AEs) that occur during the 6 months from the first dose of Xeljanz. The efficacy endpoints will be the modified Disease Activity Score using 28 joint counts (DAS28) change from baseline, [European League Against Rheumatism](#) (EULAR) response, and American College of Rheumatology 20% improvement criteria (ACR20) response after treatment (see [Section 7.3](#)).

### 7.2. Setting

#### 7.2.1. Inclusion criteria

To be included in the study all patients will have received at least 1 dose of Xeljanz for the treatment of the following indication as per local labelling:

Patients must meet all of the following inclusion criteria to be eligible for inclusion in the study:

- Moderately to severely active RA in adult patients who have had an inadequate response or intolerance to methotrexate.
- Active psoriatic arthritis (PsA) in adult patients who have had an inadequate response or intolerance to previous antirheumatic drugs (DMARDs)
- Evidence of a personally signed and dated informed consent document indicating that the patient (or a legally acceptable representative) has been informed of all pertinent aspects of the study. (In case of subjects to be collected data retrospectively, whether or not to obtain the informed consent document depends on the decision by the institutional review board (IRB)/independent ethics committee (IEC)).

[figure not shown]
#### **7.2.2. Exclusion criteria**

Patients meeting any of the following criteria as per the local labeling will not be included in the study:

1. Patients with a history of hypersensitivity to any ingredients of this product.
2. Patients with serious infection (sepsis, etc.) or active infection including localized infection.
3. Patients with active tuberculosis.
4. Patients with severe hepatic function disorder.
5. Patients with an absolute neutrophil count (ANC) <1,000 cells/mm^3.
6. Patients with an absolute lymphocyte count (ALC) <500 cells/mm^3.
7. Patients with a hemoglobin level <9 g/dL.
8. Pregnant or possibly pregnant women.
9. Because of lactose contained in this drug, it should not be administered to patients with hereditary problems of galactose intolerance, Lapp lactase deficiency or glucose-galactose malabsorption.

#### **7.2.3. Duration of the study**

CCI

[figure not shown]

The re-examination period is from 02 April 2014 to 01 April 2020, and the final re-examination report should therefore be submitted by 01 July 2020. Additional safety and effectiveness result

report from prospective and retrospective studies until 26 June 2022 would be submitted as part of RMP.

CCI

### 7.2.5. Study procedures

The investigator should enroll all patients to whom Xeljanz is prescribed for the first time according to the local product document and who agree to participate in this study by signing the data privacy statement (used in place of the informed consent form) by continuous registration method. In case of the patients who already have been administered Xeljanz but not participated in this study, study related information from the first administration until the last day of the observation period should be collected retrospectively. Xeljanz tablets will be medicated by the investigator's prescription under usual clinical practice. Pfizer Korea will not provide the medicinal product for this study.

There will be no mandatory visit during the study. The investigators will collect relevant data from the time of initiating administration of Xeljanz until 6 months of treatment. If the patient does not complete 6 months of treatment, relevant data should be collected based on the last assessment performed at the time of treatment discontinuation. The investigator should record the following information on the patient's CRF:

#### 7.2.5.1. Information of institution

The following will be recorded on the CRF for each patient:

- Name of institution: Enter the code number assigned to each institution.
- Patient number: The investigator will sequentially assign each patient a patient identification number, which will be a 4-digit number. The total number of cases that need to be collected will be allocated to each study site by Pfizer at the time of execution of a contract with each site.
- Completion of the study: If the patient completed 6 months treatment, check "yes". Otherwise, check "no" and choose reason for the discontinuation: AE; lack of efficacy; others.

- Date of CRF completion: Record the date of CRF completion.
- Signature of investigator: Contracted investigator must sign after identifying the CRF.
- Confirmation of data privacy statement: If the patient has signed the data privacy statement to indicate agreement for using his/her personal and medical information, check the box of “yes” on the CRF in case of subjects to be collected data prospectively. If not, check “no” and exclude the case from the study. If the patient has signed the data privacy statement, check the box of “yes” on the CRF in case of subjects to be collected data retrospectively, and if not, check “no” on the CRF and check if it is available for the exempt of the data privacy statement according to the IRB/IEC’s decision

#### **7.2.5.2. Demography and baseline characteristics**

The following will be recorded on the CRF for each patient:

- Age: Record actual age of the patient at the time of enrollment in case of subjects to be collected data prospectively. Record age of the patient at the first dosing of Xeljanz in case of subjects to be collected data retrospectively. The age should be calculated by the year of birth.
- Sex: Check the box next to “male” or “female” on the CRF.
- Height: Record by unit of ‘cm’ in case of subjects to be collected data prospectively. Check the box indicated to the range of height(unit of ‘cm’) in case of subjects to be collected data retrospectively
- Weight: Record by unit of ‘kg’ in case of subjects to be collected data prospectively. Check the box indicated to the range of weight(unit of ‘kg’) in case of subjects to be collected data retrospectively
- Herpes zoster vaccination: Record if the patient had received vaccine of herpes zoster: yes; no; unknown.
- Smoking: Record smoking status of the patient: ex-smoking; current smoking; non-smoking; unknown.
- Duration of the disease: Record the duration of disease since the date that the patient was initially diagnosed with RA and PsA.
- Severity of disease activity:

RA: Disease activity should be assessed by initial DAS28. DAS28  $>5.1$  is considered to be indicative of high disease activity; DAS28  $>3.2$  and  $\leqslant 5.1$  indicates moderate disease activity; DAS28  $\leqslant 3.2$  indicates low disease activity. A patient scoring less than 2.6 is defined as being in remission.

PsA: Disease activity should be assessed by initial DAS28. DAS28 >5.1 is considered to be indicative of high disease activity; DAS28 >3.2 and ≤5.1 indicates moderate disease activity; DAS28 ≤3.2 indicates low disease activity. A patient scoring less than 2.6 is defined as being in remission.

- Radiologic progression: Radiologic progression based on clinically relevant evaluation methods, such as X-ray, ultrasonography, or magnetic resonance imaging, should be recorded, if evaluated.
- Previous treatments: Only record RA and PsA treatments received 6 months prior to the initiation of Xeljanz. Record name of the medication/therapy, route and duration of the administration, and overall response, if possible.
- Latent tuberculosis: Record if the patient has latent tuberculosis: yes; no; unknown.
- Renal disorder: Record if the patient has renal disorder: yes (severe/moderate/mild); no.
- Hepatic disorder: Record if the patient has hepatic disorder: yes (severe/moderate/mild); no.
- Other past/present diseases: Record “yes” or “no” for medical history. If “yes”, record adequate full name of the past or present disease according to the Medical Terminology Dictionary written by the Korean Medical Society. Past or present disease will be determined based on the date of the first dose of Xeljanz.
- Allergic history: Check either “yes” or “no” on the CRF. If “yes”, record the trigger factors and the corresponding symptoms.

#### **7.2.5.3. Administrative status for medicinal product**

The following will be recorded on the CRF for each patient:

- Treatment duration: Record start date and stop date (year/month/day) of the treatment of Xeljanz. If the medication is being continued at the completion of the study, record the start date only.
- Daily dose: Record total daily dose of Xeljanz in mg.
- Daily dosing frequency: Record dosing frequency per day.
- Reason for dose adjustment: If there are any dose adjustments during the study, record the reason(s).

#### **7.2.5.4. Concomitant treatments**

Any concomitant treatments should be recorded on the CRF for each patient. The information should include:

- Name of the drug: Record generic name of the concomitant medication.
- Daily dose: Record total daily dose of the concomitant medication.
- Duration of the treatment: Record the start date and stop date (year/month/day) of the concomitant medication. If the medication is being continued at the completion of the study, record the start date only and check “ongoing”.
- Purpose of the treatment: Record purpose of the concomitant treatment in detail.

#### **7.2.5.5. Safety and efficacy data**

Please refer to [Section 7.3](#) for safety and efficacy assessment and data collection.

### **7.3. Variables**

#### **7.3.1. Safety variables**

Safety will be assessed by the investigator based on AEs that occur during 6 months from the first treatment for all patients who have received at least 1 dose of Xeljanz according to the local product document.

##### **7.3.1.1. Adverse events**

Please refer to [Section 9](#) for the definition of non-serious and serious adverse events (SAEs).

Any AEs observed and reported within the reporting period will be recorded on the CRF by the investigator, regardless of the causal relationship with Xeljanz (see [Section 9.2](#)). The AEs can be reported by the patients. The investigator will also collect AE data by asking the patient questions such as “Have you had any health problem since the last visit?”

Check either “yes” or “no” in the AE section of CRF. If “yes”, record the following information:

Event name: Record the name of the AE according to the Korean Version of World Health Organization - Adverse Reaction Terminology (WHO-ART) distributed by Korean Ministry of Health and Welfare. If there is no not an appropriate term in the WHO-ART, record the name of the AE according to the Medical Terminology Dictionary written by the Korean Medical Society. If possible, specify diagnosis, not individual symptoms.

Date of onset: Record the onset date of the AE. Record approximate date if an actual date is unknown.

Date of recovery: Record the stop date of the AE if the outcome of the AE is recovered or recovered with sequelae (see below). Record approximate date if an actual date is unknown.

Seriousness: Check either “yes” or “no” to indicate if the event is a SAE. If “yes” record appropriate category of the seriousness (see [Section 9](#) for the definition and reporting of SAEs).

**Severity:** Evaluation of AE severity must be done according to the following categories:

- Mild: Not causing any significant problem to the patient. Administration of medicinal product continues without dose adjustment.
- Moderate: Causes a problem that does not interfere significantly with usual activities or the clinical status. Dose of the medicinal product is adjusted or other therapy is added due to the AE.
- Severe: Causes a problem that interferes significantly with usual activities or the clinical status. The medicinal product is stopped due to the AE.

If the severity of an AE changes, the AE must be entered separately. Record the stop date of the previous severity and onset date of the new severity – along with completion of all other related items.

**Causality assessment:** The causal relationship of AEs to the medicinal product must be allocated by the investigator according to the following criteria in alignment with the requirements of MFDS:

- Certain
  - It follows a reasonable time sequence from administration of the drug (before and after the study medication);
  - It could not be explained by other drugs, chemical substances or accompanying diseases;
  - It has clinically reasonable reaction on cessation of the drug;
  - It has pharmacological or phenomenological reaction to re-administration of the drug, where necessary.
- Probable/likely
  - It follows a reasonable time sequence from administration of the drug (before and after the study medication);
  - It could not be explained by other drugs, chemical substances or accompanying diseases;
  - It has clinically reasonable reaction on cessation of the drug (no information on re-administration).
- Possible
  - It follows a reasonable time sequence from administration of the drug;

- It could also be explained by other drugs, chemical substances or accompanying diseases;
- It lacks information or has unclear information on discontinuation of the drug.
- Unlikely
  - It is not likely to have a reasonable causal relationship from administration of the drug. Rather, it seems to be temporary;
  - It could also be reasonably explained by other drugs, chemical substances or latent diseases.
- Conditional/unclassified
  - It needs more data to make an appropriate assessment or its additional data are being reviewed.
- Unassessible/unclassifiable
  - Lack of sufficient information or conflicting information hampers accurate causality assessment or supplementation or confirmation.

All AEs, except for those with a causality of “unlikely”, are considered as AEs whose causal relationship to the study drug can not be excluded (ie, adverse drug reaction [ADR]).

Action taken: With regard to the medicinal product, actions will include:

- Permanently discontinued;
- Temporarily discontinued or delayed;
- Dose reduced;
- Dose increased;
- No change;
- Not applicable.

Outcome: Evaluation of outcome will include:

- Recovered;
- Recovered with sequelae;
- Recovering;

- Not recovered;
- Unknown.

Please refer to [Section 9](#) for the requirements for reporting safety events to Pfizer Safety during the study.

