**Table 1 Recommended Laboratory Test**

	Lymphocyte	Neutrophils	Hemoglobin	Lipids (TC, HDL, LDL)
Baseline	√	√	√	√
4 to 8 weeks after treatment		√	√	√
Every 3 months	√	√	√	

Abbreviations: TC=total cholesterol, HDL= high density lipoprotein, LDL=low density lipoprotein.

In case there are any clinically significant laboratory abnormalities (as per the investigator's judgment) that occur after the treatment of Xeljanz compared to baseline, the tests should be recorded in detail on the CRF, including the laboratory normal ranges of the center, test results before and after Xeljanz treatment, a causal relationship to Xeljanz, and any comments from the investigator.

According to Contraindication on label, the investigator should discontinue the patient's treatment if the laboratory test results are as below

- Patients with an absolute neutrophil count (ANC) <500 cells/mm^3\*
- Patients with a hemoglobin level <8 g/dL

Please refer to [Section 9.4.1](#) for the criteria for determining whether an abnormal objective test finding should be reported as an AE.

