6.4. Safety Analyses

Safety analyses will be performed based on data of safety analysis set. All adverse events in CRF will be classified by System Organ Class (SOC) and Preferred Term (PT) according to the latest version of MedDRA.

- 1) All adverse events investigated after administration of Xeljanz® during the study will be summarized by frequency and percent (n, percentage) by categorizing as follows. Also, it will be presented in n, incidence rate, 95% confidence interval of incidence rate and number of events for each SOC and PT.
 - Frequency analysis of adverse events/adverse drug reactions
 - Frequency analysis of serious adverse events/serious adverse drug reactions
 - Frequency analysis of serious unexpected adverse events/serious unexpected adverse drug reactions
 - Frequency analysis of unexpected adverse events/unexpected adverse drug reactions
 - Frequency analysis of adverse events of special interest/adverse drug reactions of special interest
 - Occurrence status of adverse events/adverse drug reactions by its seriousness
 - Results in death
 - Is life-threatening
 - Requires inpatient hospitalization or prolongation of hospitalization
 - Results in persistent or significant disability/incapacity
 - Results in congenital anomaly/birth defect
 - Important medical event: if it is determined that the event may jeopardize the patient or may require intervention to prevent one of the other outcomes listed in the definition above
 - Occurrence status of adverse events/adverse drug reactions by its severity
 - Mild
 - Moderate
 - Severe
 - Occurrence status of adverse events/adverse drug reactions by its causality assessment
 - Related to this medicinal product: ① Certain

Statistical Analysis Plan

- ② Probable/likely
- ③ Possible
- ⑤ Conditional/unclassified
- ⑥ Unassessable/unclassifiable

- Not related to this medicinal product: ④ Unlikely
- Occurrence status of adverse events/adverse drug reactions by its action taken
 - Permanently discontinued
 - Temporarily discontinued or delayed
 - Dose reduced
 - Dose increased
 - No change
 - Not applicable
- Occurrence status of adverse events/adverse drug reactions by its outcome
 - Recovered
 - Recovered with sequelae
 - Recovering
 - Not recovered
 - Unknown

2) Occurrence status of adverse events by demography and baseline characteristics

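### Each adverse event severity grade joins clinical impact to drug action with no rule for conflicts, so the severity table mixes the two.

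*Protocol*

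**What the plan says.** The Severity item of Protocol 7.3.1.1 makes the scale compulsory: "Evaluation of AE severity must be done according to the following categories". Each of the three grades then has two parts.

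- The lowest grade: "Mild: Not causing any significant problem to the patient. Administration of medicinal product continues without dose adjustment".
- The middle grade opens with "Moderate: Causes a problem that does not interfere significantly with usual activities or the clinical status" and continues with "Dose of the medicinal product is adjusted or other therapy is added due to the AE".
- The top grade: "Severe: Causes a problem that interferes significantly with usual activities or the clinical status. The medicinal product is stopped due to the AE".

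An event whose severity changes must be entered again as a separate record, with a stop date for the old grade and an onset date for the new one.

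Action taken is a separate CRF item in the same section. It has six categories and covers only actions on the medicinal product. Stopping is split into a permanent category and "Temporarily discontinued or delayed".

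SAP 4.4 lists severity among five attributes of the safety endpoint. SAP 6.4 item 1 includes "Occurrence status of adverse events/adverse drug reactions by its severity" and a separate table by action taken, and reports the number of events by SOC and PT. It names the three grades without defining them.

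**The concern.** Clinical impact and drug action are different things and need not agree. The protocol neither joins the two sentences of a grade with an explicit rule nor ranks them. An investigator whose event meets the impact sentence of one grade and the action sentence of another has to choose, and two sites can choose differently while both comply.

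At stake is what the severity table means. A reader will take the Severe row as a statement of how ill patients were. As written, it is partly a statement about whether the drug was stopped, which the action-taken table already shows. The separate-entry rule carries the problem one step further. If grade follows action, a dosing change with no change in the patient's condition can produce a new record.

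**Working it through.** The plan gives no figure to reproduce, so the check is on the definitions.

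**Inputs (Protocol 7.3.1.1)**

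| Grade | Impact part | Action part |
|---|---|---|
| Mild | no significant problem | drug continued, dose unchanged |
| Moderate | problem without significant interference | dose adjusted, or other therapy added |
| Severe | significant interference | drug stopped |

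Drug action has five substantive categories (permanent stop, temporary stop or delay, reduced, increased, no change) plus Not applicable. Added therapy is yes or no. The count treats the three impact levels as mutually exclusive.

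**Step 1. Combinations.** 3 impact levels × 5 actions × 2 therapy states = 30. With Not applicable included, 3 × 6 × 2 = 36.

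**Step 2. Both sentences required.** First count a temporary stop as stopped and let Mild allow added therapy.
- Mild: no change, either therapy state = 2.
- Moderate: reduced or increased with either therapy state = 4, plus added therapy with a permanent stop, a temporary stop or no change = 3, giving 7.
- Severe: permanent or temporary stop with either therapy state = 4.
- Total graded: 2 + 7 + 4 = 13, so 30 − 13 = 17 fit no grade.

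If a temporary stop does not count and Mild excludes added therapy, the total graded is 1 + 7 + 2 = 10, and 20 fit no grade. The range is 17 to 20 of 30 (22 to 25 of 36). None fits two grades.

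**Step 3. Either sentence suffices.** Every combination now fits at least one grade. Over the same variations, 7 to 11 of 30 fit one grade, 18 to 20 fit two and 1 to 3 fit all three. Of 36, 20 to 22 fit two and 1 to 3 fit three.

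**Step 4. Two plain cases.**
- An event interferes significantly, the drug continues unchanged and no therapy is added. It is Severe by impact and Mild by action.
- A problem is significant enough not to be Mild but does not interfere significantly, with no dose change and no added therapy. It is Moderate by impact and Mild by action.

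Each fits no grade under Step 2 and two grades under Step 3.

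**Step 5. Effect on the Severe count.** Let S be the events with a drug stop, I the events with significant interference, and B those with both. The Severe count is S by action, I by impact, B if both are required, and S + I − B if either suffices. These agree only when the stops and the interfering events are the same events. The documents give no values for S, I or B. If both sentences are required, every Severe event is a drug stop and every Mild event is on unchanged dose, so the severity table partly repeats the action-taken table.

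**Step 6. Event counts.** A changed grade means a new record, and SAP 6.4 does not say whether such records are merged before events are counted. A dosing change alone could therefore raise the number of events for a term.

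**Step 7. What is untouched.** The proportion of patients with any adverse event does not depend on grade. Seriousness and causality have their own criteria. SAP 6.4 items 2 to 4 (subgroup tests and logistic regression) concern the occurrence of events and do not name severity as an outcome or factor.

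**The case against.** The case for leaving the text alone, or doing less, has several parts.

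**The impact sentence is broader than daily activities.** It also covers clinical status. A laboratory value that triggers the rule in 7.3.1.2, where "the investigator should discontinue the patient's treatment if the laboratory test results are as below", might be judged to interfere significantly with clinical status even without symptoms. Impact and action would then agree on Severe. This stands, so the laboratory stop is an arguable example and the point does not rest on it. The two cases in Step 4 do not depend on it.

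**The action part carries information of its own.** Added therapy appears in Moderate but not in the action-taken categories. A reader might infer that the action sentences are redundant. They are not; the overlap is partial. Concomitant treatments and their purpose are recorded under 7.2.5.4, but not as an attribute of the event.

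**Impact alone is not perfectly clean.** Mild and Moderate are worded closely enough that a minor problem could meet both. This stands. The exclusive levels assumed in the count are not fully secured by the text, so any rewording must separate these two grades.

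**It is late.** The current text is Amendment 11, dated 26 Apr 2022, and Protocol 7.1 runs retrospective collection until 26 June 2022. A new definition would reach few cases and would need IRB/IEC approval. This limits the protocol change but not the SAP change.

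**The regulator may prescribe the scale.** Protocol 7.9 says the protocol is determined by MFDS regulation. Within 7.3.1.1, only the causality criteria are tied to MFDS requirements. Whether the severity wording is also prescribed cannot be settled from the documents.

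**Conclusion.** The defect is real and confined. The severity scale is compulsory, has two parts per grade and lacks a rule for disagreement; neither document supplies one elsewhere. Compliant sites can grade the same event differently, and the severity table mixes impact with drug action. The number of events may also be affected through the separate-entry rule.

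The counts of 17 to 20 ungraded and 18 to 20 doubly graded combinations out of 30 come from two different readings of the text and cannot both apply to one grading. They describe the scale, not patients, and assume mutually exclusive impact levels.

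Two stronger conclusions are tempting. A reader might infer that discordant events are common; the documents give no event frequencies, so this cannot be said. A reader might also infer that the primary safety result is compromised; the main measure is adverse event incidence, and the proportion of patients with any event does not use the scale. This is a measurement flaw in one descriptive table of a non-comparative study, and it is worth correcting because the remedy is cheap.

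**What to change.** 1. **SAP 6.4, for all cases.** Add a cross-table of severity by action taken for adverse events and adverse drug reactions. State beside the severity table that recorded grades combine impact and action, so that Severe is not read as clinical impact alone. Count an event re-entered only because its grade changed as one event, and say which of its grades is tabulated. The fields are already on the CRF. The cost is one table, one note and one counting rule, with no new data.

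2. **Protocol 7.3.1.1, for any cases still to be graded.** State that the impact sentence governs, and word Mild and Moderate so that they do not overlap. Leave drug action to its own field and added therapy to the concomitant-treatment record. The cost is an amendment with its approvals. Earlier cases keep the old grading, so the severity table should then be shown by grading version.

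If no cases remain to be graded, item 1 alone is enough. Neither item changes a dosing or stopping rule.
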